Appendix I: Schedule of assessments and Procedures

QMS Document Name: Statistical Analysis Plan	Page 29 of 33
QMS No (include version ref): STF-015-GL.02	Document date: 09JUL2019
CONFIDENTIAL	

Appendix II: Programming Conventions for Outputs

❖ Clinipace Output Conventions

Outputs will be presented according to the Clinipace general guidelines and template for outputs conventions.

❖ General Rules

The following conventions will be applied for reporting descriptive statistics of all continuous data.

Mean, Median, Q1, Q3, Minimum, and Maximum will have the same precision as Raw data (number of digits) for non-derived data (e.g. weight).

SD will be presented with one digit more than mean.

Statistics on derived data (e.g. treatment exposure time in days) will be rounded to reasonable number of digits.

Qualitative variables will be summarized by counts and percentages. Unless otherwise stated, the calculation of proportions will be based on the number of available subjects. Therefore, counts of missing observations will be included in the denominator and presented as a separate category.

Total of missing and non-missing observations at each time-point will reflect the population still in the trial at that time. For example, if a subject is still in the trial at the time-point but with missing data, it should be counted in the number of missing observations.

❖ Dates & Times

Depending on data available, dates and times will take the form DDMMYYYY and HH:MM.

❖ Spelling Format

English US

❖ Presentation of Treatment Groups

All listings will be ordered by the following (unless otherwise indicated in the template):

- Treatment group
- Center-subject ID
- Date (where applicable)

All tables containing coded terms (CM, MH, AE), coded records will be sorted in frequency order.

QMS Document Name: Statistical Analysis Plan	Page 31 of 33
QMS No (include version ref): STF-015-GL.02	Document date: 09JUL2019
CONFIDENTIAL	

Appendix III: Partial Date Conventions

- Algorithm for Treatment Emergence of Adverse Events:

START DATE	STOP DATE	ACTION
Known	Known	If start date < study med start date, then not TEAE. If start date \geq study med start date, then TEAE.
	Partial	If start date < study med start date, then not TEAE. If start date \geq study med start date, then TEAE.
	Missing	If start date < study med start date, then not TEAE. If start date \geq study med start date, then TEAE.
Partial, but known components show that it cannot be on or after study med start date	Known	Not TEAE
	Partial	Not TEAE
	Missing	Not TEAE
Partial, could be on or after study med start date	Known	If stop date < study med start date, then not TEAE. If stop date \geq study med start date, then TEAE.
	Partial	Impute stop date as latest possible date (i.e. last day of month if day unknown or 31st December if day and month are unknown), then: If stop date < study med start date, then not TEAE. If stop date \geq study med start date, then TEAE.
	Missing	Assumed TEAE
Missing	Known	If stop date < study med start date, then not TEAE. If stop date \geq study med start date, then TEAE.
	Partial	Impute stop date as latest possible date (i.e. last day of month if day unknown or 31st December if day and month are unknown), then: If stop date < study med start date, then not TEAE. If stop date \geq study med start date, then TEAE.

QMS Document Name: Statistical Analysis Plan	Page 32 of 33
QMS No (include version ref): STF-015-GL.02	Document date: 09JUL2019
CONFIDENTIAL	

START DATE	STOP DATE	ACTION
	Missing	Assumed TEAE.

QMS Document Name: Statistical Analysis Plan	Page 33 of 33
QMS No (include version ref): STF-015-GL.02	Document date: 09JUL2019
CONFIDENTIAL

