Statistical Methods:	
Safety Analyses
 
All safety analyses will be performed on the safety analysis set (SAS).
 
Adverse events will be coded by System Organ Class and Preferred Term using the current version of MedDRA. Incidences of treatment-emergent AEs (TEAEs), ie, events that started after exposure to study drug or worsened in severity after dosing, will be presented by dose group. Incidences of TEAEs will also be presented by maximum severity and relationship to study medication.
 
Safety data will be summarized through appropriate data tabulations, standard descriptive statistics, and graphical presentations. For each continuous laboratory parameter, results will be categorized as low, normal, or high based on the laboratory normal ranges. Frequencies and percentages will be presented by dose group for subjects who had a shift to low and for subjects who had a shift to high from baseline to any post-dosing assessment.
 
The association of AEs, clinical laboratory tests, vital sign measurements with the actual dosing of study drug or systemic exposure of LT5001 drug product may also be explored. If appropriate, statistical modeling will be performed to further characterize the associations mentioned above. All out-of-range and clinically significant laboratory results will be identified in subject data listings. The number and percentage of subjects in each dose group with normal and abnormal physical examination results will be presented for evaluations at baseline and final visit.
 
For each body system, changes in the subjects' findings from baseline to final visit (no change, normal to abnormal, or abnormal to normal) will be tabulated for each dose group.
 
Pharmacokinetics Analyses

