9 ADVERSE EVENTS

An AE is defined as any untoward medical occurrence in a patient administered a pharmaceutical product during the course of a clinical investigation. An AE can therefore be any unfavorable and unintended sign, symptom, or disease temporally associated with the use of a study drug, whether or not thought to be related to the study drug.

Each AE will be collected from the signing of the ICF until the follow-up/end-of-study visit. Adverse events that are identified at the last assessment visit (or the early termination visit) must be recorded on the AE eCRF with the status of the AE noted. All events that are ongoing at this time will be recorded as ongoing on the eCRF. If the Investigator indicates the AE is “probably”, “possibly”, or “definitely” related to the study drug, the AE must be followed until they are resolved or medically stable, or until reasonable attempts to determine resolution of the event are exhausted. The investigator should use his/her discretion in ordering additional tests as necessary to monitor the resolution of such events.

The procedures specified in [Section 9.4](#) are to be followed for reporting SAEs.

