10.6 Safety Analysis

All safety analysis will be performed on the SAS for both Part A and Part B.

Adverse events will be coded by System Organ Class and Preferred Term using the current version of MedDRA. Incidences of TEAEs (ie, events that started after 1st dose of the study drug or worsened in severity after 1st dosing), will be presented by dose group. Incidences of TEAEs will also be presented by maximum severity and relationship to study medication.

Safety data will be summarized through appropriate data tabulations, standard descriptive statistics, and graphical presentations. For each continuous laboratory parameter, results will be categorized as low, normal, or high based on the laboratory normal ranges. Frequencies and percentages will be presented by dose group for patients who had a shift to low and for patients who had a shift to high from baseline to any post-dosing assessment.

The association of AEs, clinical laboratory tests, vital sign measurements with the actual dosing of the study drug or systemic exposure of LT5001 drug product may also be explored. If appropriate, statistical modeling will be performed to further characterize the associations mentioned above. All out-of-range and clinically significant laboratory results will be identified in patient data listings. The number and percentage of patients in each dose group with normal and abnormal physical examination results will be presented for evaluations at baseline and final visit.

For each body system, changes in the patients' findings from baseline to final visit (no change, normal to abnormal, or abnormal to normal) will be tabulated for each dose group.

Application site examination (observed and change from baseline) will be summarized by time point using appropriate descriptive statistics.

The number and percentage of patients reporting any treatment-emergent AE will be tabulated by system organ class and preferred term (coded using MedDRA). Treatment-emergent AEs will be further classified by severity and relationship to treatment.

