5.3 Observation and analysis times

Reference Start Date and Study Day

Reference start date is defined as the day of randomization and study day relative to the reference start date will appear in every listing where an assessment date or event date appears.

Study day will be calculated from the reference start date and will be used to show start/stop day of the assessments and events relative to the first administration of study treatment.

- If the date of the event is on or after the reference date, then:

$$\text{Study day} = (\text{date of event} - \text{reference date}) + 1.$$
- If the date of the event is prior to the reference date, then:

$$\text{Study day} = (\text{date of event} - \text{reference date}).$$

In case of that event date is partial or missing, the date will appear partial or missing in the listings, and Study Day, and any corresponding durations will be presented based on the imputations specified in Appendix III; Partial Date Conventions.

Definition of baseline values

The baseline value is defined to be the last value which was assessed before the 1st dose of study medication.

Clinical laboratory data on day 1 (Visit 1) will serve as baseline.

Baseline NRS will use the mean NRS score in the 7-days run-in period.

Baseline of 5D itch and Skindex-10 score will be assessed at Visit 1.

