11.1 Adverse events

All AEs will be coded using the Medical Dictionary for Regulatory Activities (MedDRA) Version 22.0 (or later).

Adverse events will be grouped by system organ class (SOC) and PT and summarised by treatment. The summary tables will present the number and percentage of subjects with AEs and number of events, by SOC and by PT for each treatment group.

All AE summaries will be restricted to Treatment-emergent adverse events (TEAEs) only.

A treatment emergent adverse events (TEAE) is defined as any AE with an onset date on or after the first dose of study treatment if the AE was absent before the first dose of study treatment, or pre-existing medical condition worsens after the first dose of study treatment.

For the summaries of AEs, subjects who experience the same AE (in terms of the MedDRA SOC and

QMS Document Name: Statistical Analysis Plan	Page 19 of 33
QMS No (include version ref): STF-015-GL.02	Document date: 09JUL2019
CONFIDENTIAL	

PT) more than once will only be counted once for that event in the number of subjects but all occurrences of the same event will be counted in the number of events.

For analysis, at AE level, the worst severity and the strongest relationship to trial treatment will be assigned to the AE if the severity and relationship changes overtime for the AE with the same AE ID. At subject level, a subject with the same AE term being reported multiple times, the maximum severity and the strongest relationship to trial treatment will be tabulated.

Study drug related TEAEs are defined as TEAEs with definitely, probably, or possibly relationship with study drug

Nature and severity of adverse event (AEs) and number of patients with AEs will be analysed as primary endpoint in part A and secondary endpoints of Part B.

An overview table of TEAEs will be provided detailing the number and percentage of subjects along with the number of reported events with

- Any TEAE
- TEAEs by severity (Mild, Moderate, Severe)
- Any TEAE related to study drug
- Any serious TEAE
- Any serious TEAE, related to study drug
- Any TEAE leading to discontinuation of study drug
- Any TEAE leading to death

Summary tables will also be provided for TEAEs, TEAE by severity, study drug related TEAEs, TEAEs leading to discontinuation of study drug, and TEAEs leading to death, detailing the number and percentage of subjects and number of events by MedDRA SOC (ordered by frequency) and PT (ordered by frequency).

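### The date table in SAP Appendix III drops adverse events that began before dosing and worsened on treatment, although the protocol and SAP 11.1 count them as treatment-emergent

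*SAP*

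**What the plan says.** Three places define treatment emergence, and each has a worsening limb:

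- Protocol synopsis, Statistical Methods: "events that started after exposure to study drug or worsened in severity after dosing".
- Protocol 10.6: "events that started after 1st dose of the study drug or worsened in severity after 1st dosing".
- SAP 11.1: onset on or after first dose, "or pre-existing medical condition worsens after the first dose of study treatment".

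SAP Appendix III then gives a table, labelled as the algorithm for treatment emergence, that crosses four kinds of start date with three kinds of stop date. For a known start date, all three stop-date rows say "If start date < study med start date, then not TEAE". For a start date described as "Partial, but known components show that it cannot be on or after study med start date", all three rows give the same negative result. No row mentions severity.

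The only reference to the appendix in the SAP text is in SAP 5.3, in a sentence that begins "In case of that event date is partial or missing, the date will appear partial or missing in the listings" and sends the reader to the appendix for study day and durations.

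Two other provisions matter. Protocol section 9 says "Each AE will be collected from the signing of the ICF until the follow-up/end-of-study visit", so pre-dose events are in the data. SAP 11.1 says "All AE summaries will be restricted to Treatment-emergent adverse events (TEAEs) only".

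**The concern.** The table and the definitions classify the same event differently. Take an event that starts during screening, is mild at Day 1 and becomes severe in Week 2. It meets the protocol definition of a TEAE, but the table returns the opposite. A programmer who implements the table, which is the only step-by-step rule in the SAP, would leave it out.

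The loss goes beyond overall incidence. The tables of TEAEs by severity, of serious TEAEs and of TEAEs leading to discontinuation or death all depend on the same flag. A pre-dose event that became serious on treatment would be in the listings and absent from the tables. Adverse events are the Part A primary endpoint and a Part B secondary endpoint, and the Part A interim analysis that the DSMB reviews before Part B follows this SAP. For this class of event the error can only undercount.

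**Working it through.** There is no stated figure to reproduce. The check compares the two rules case by case.

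**Structure of the table.** 4 start-date categories × 3 stop-date categories = 12 cells.

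| Start date | Cells | Result for a pre-dose start |
|---|---|---|
| Known | 3 | never a TEAE |
| Partial, certainly pre-dose | 3 | never a TEAE |
| Partial, ambiguous | 3 | 2 decided by stop date, 1 assumed TEAE |
| Missing | 3 | 2 decided by stop date, 1 assumed TEAE |

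So 6 of the 12 cells return a negative result once a pre-dose start is established (the three known-start cells return TEAE only for a start on or after dosing). The other 6 can return TEAE: 4 by stop date and 2 by assumption. An ongoing event can therefore be a TEAE if its start date is incomplete and not a TEAE if the same date is complete.

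**Where the two rules disagree.** Rule D (the definition): TEAE if onset is on or after first dose, or if the event worsens after it. Rule T (the table): as above. An event that stopped before dosing cannot worsen on treatment, so that combination is omitted for worsened events.

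| Start | Stop | Worsened after dose? | Rule T | Rule D |
|---|---|---|---|---|
| Known, pre-dose | post-dose | yes | not TEAE | TEAE |
| Known, pre-dose | missing | yes | not TEAE | TEAE |
| Partial, certainly pre-dose | post-dose | yes | not TEAE | TEAE |
| Partial, certainly pre-dose | missing | yes | not TEAE | TEAE |

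Of 14 combinations checked (known pre-dose 5, certainly pre-dose 5, known post-dose 4), these 4 disagree and the other 10 agree. Adding a worsening branch to the pre-dose rows brings the 4 to 0.

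**Can such events arise?** Protocol 8.1 puts the 7-day diary run-in after consent, and protocol 5.1 allows screening up to 28 days before Day 1. Each patient therefore has between 7 and 28 days in which an adverse event can be entered before dosing. SAP 11.1 also provides for severity that changes over time under one event identifier, so a worsened event may keep its original record and start date.

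**Scale per patient**, for a patient with no other TEAE, as 1/n:

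- Part A, LT5001: 1/12 = 8.3 points.
- Part A, placebo: 1/6 = 16.7 points.
- Part B at 45 per arm (protocol): 1/45 = 2.2 points.
- Part B at 30 per arm (SAP): 1/30 = 3.3 points.

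These show how far one patient moves the incidence. They do not predict how many patients are affected.

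**The case against.** Several arguments limit the point.

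- **Scope of the appendix.** It is headed as a convention for partial dates, and its only cross-reference concerns partial or missing dates. The formal definition sits in 11.1, so the known-date rows could be read as completing a grid for the onset limb only. That is a sensible reading, but the SAP does not state it. The table carries the label of the emergence algorithm and rules on fully known dates.
- **Wording of SAP 11.1.** It speaks of a pre-existing condition rather than a pre-dose adverse event. A medical-history condition that worsens and is first entered as an event after dosing has a post-dose start, and the table then agrees with 11.1. This narrows the problem to events already entered between consent and Day 1. Those fall squarely under the protocol wording and naturally under 11.1.
- **The CRF is not available.** If each severity change is a new dated row, the worsened row has a post-dose start and is captured. This stands as a limit on the consequence. No rule in the documents requires such a row, and protocol 9.1 lists one intensity assessment per event with no dated history.
- **6 of 12 cells overstates the reach.** Fair: real disagreement needs worsening and a post-dose or missing stop date, which gives the 4 combinations above. Treating ambiguous dates as TEAE is ordinary conservative practice and not a separate error.
- **Other outputs catch worsening.** Listings (SAP 11.1), vital-sign changes (11.3), laboratory shifts (11.4), physical-examination shifts (11.5), and application-site and ROAT tables (11.6) do not use the TEAE flag. Skin findings noted at the screening examination and first entered as events after dosing are also still TEAEs. So the local-tolerance data do not rest on this flag alone.

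**Conclusion.** The concern holds. The table gives a result that the protocol and SAP 11.1 contradict for a worsened event with an established pre-dose start, and no text says which prevails. The SAP's statement in 2.1 that it is consistent with the protocol does not rank one of its sections against another.

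Confidence in the textual conflict is high. The loss of events from the summaries rests on two assumptions: that the table is programmed literally, and that a worsened event keeps its original record and start date. The documents give no adverse event rate, so the number affected is unknown and may be small. With arms of 12 and 6 in Part A, even one patient is visible in the primary endpoint, and the direction is always downward.

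**What to change.** 1. In Appendix III, add a row ahead of the date rows. An event with a pre-dose start whose severity increases on or after first dose, compared with its last pre-dose severity, is a TEAE. Its reported severity is the worst post-dose grade. Reconcile this with the existing SAP 11.1 rule, which assigns the worst severity under an event identifier without separating pre-dose from post-dose grades.
2. State that SAP 11.1 governs treatment emergence and that the date rows decide only the onset limb.
3. If the CRF does not hold dated severity changes, require a post-dose increase to be entered as a new record dated at the worsening. Choose one route and state it, because a new record adds to the event count and a flag on the existing record does not.

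The cost is one row and one sentence in the SAP, some programming, and possibly a short change to the CRF completion instructions. TEAE counts may rise slightly.
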